Endpoints	
Primary endpoint:
 
 ➤ Rate of response at 6 weeks after switching from rhTPO to eltrombopag or vice versa 
Response is defined according to the Chinese guidelines for treatment of adult primary immune thrombocytopenia as ⁷:
 
Complete response (CR): platelet count $\geq 100 \times 10^9/L$ and absence of bleeding.
 
Response (R): platelet count range $30-100 \times 10^9/L$, at least doubling of the baseline count, and absence of bleeding.
 
No response (NR): platelet count $< 30 \times 10^9/L$, or less than doubling of the baseline count, or bleeding.
 
The rate of response at 6 weeks includes the total proportion of patients who achieved CR and R at 6 weeks in the groups switch from rhTPO to eltrombopag and eltrombopag to rhTPO, respectively.
 
Secondary endpoints:
 
 ➤ Rate of response at 6 weeks after switching, according to the reasons of switching 
The reasons of switching include ³:
 
Lack of efficacy:
 
 -1st TPO-RA failure: no response to either one TPO-RA administered before switch -Loss of response: relapsed after transient response to 1st TPO-RA (relapse is defined as platelet count $< 30 \times 10^9/L$, or less than doubling of the baseline count, or bleeding, after the achievement of CR or R. The blood platelet count should be confirmed on at least two separate occasions, which is at least 1 day apart when used to define relapse ⁷) 
Platelet count fluctuations: unstable platelet counts necessitating rescue therapy or transient TPO-RA dose modifications/withdrawal with associated risk of either rebound thrombocytopenia/bleeding or thrombocytosis
 
Patient's preference
 
Development of adverse events necessitating 1st TPO-RA discontinuation
 
 ➤ Proportion of patients who achieved, regained, and maintained response at 6 weeks after switching 
Response achieved refers to patients who failed the 1st TPO-RA achieve CR or R at 6 weeks after switching.
 
Response regained refers to patients who lost response to the 1st TPO-RA achieve

CR or R at 6 weeks after switching.

Response maintained refers to patients who achieved CR or R with the 1st TPO-RA and still respond to the 2nd TPO-RA at 6 weeks after switching.

- Rate of response at 3 months after switching from rhTPO to eltrombopag or vice versa

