Sample Size Justification	
Total Planned Number of Patients: 100 patients (~50 patients in each switch sequence but not a strict 1:1 ratio)
 
➤ The purpose of this study is not to compare the efficacy differences between the two switch groups but to describe the rate of response, so the sample size cannot be calculated.

	
Sample size rationale:
 
 ➤ According to a published similar literature, it is estimated that about 100 patients can reveal a certain proportion of efficacy ³; ➤ Using the cross-sectional sampling method, the estimated response rate of these two drugs is ~70% (95% CI, 50%-90%), the sample size would be 80. So, 100 patients' size was decided taking the 20% drop-out rate into consideration. ➤ According to our previous study, it is expected to complete the observation of 100 patients within one and a half year.

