Statistical Analysis	
Statistical analysis methods:
 
Statistical analysis will be conducted by SAS Version 9.2 or above. Descriptive statistics for continuous variables include minimum, maximum, mean ± standard deviation and median with inter-quartile ranges (IQR). Categorical variables will be described as frequencies and percentages. Percentage will be calculated based on non-missing data unless otherwise specified. Comparison between categorical variables will be performed using chi-square test or Fisher's exact test, while comparison between continuous variables will be performed using two-sample t test for parametric data and Wilcoxon rank sum test for non-parametric data. Logistic regression will be used to assess the association between clinical characteristics and outcome of response. Time-to-event data will be described by Kaplan-Meier survival curve with log-rank test for between-group comparison.
 
Unless specified, statistical testing will be carried out bilaterally with significance level alpha=0.05, i.e. a p-value of less than or equal to 0.05 will be considered as statistically significant. Methods of descriptive analysis and hypothesis testing will be selected according to the data characteristics. Transformations will be undertaken as needed.
 
Analysis sets:
 
Full Analysis Set (FAS): includes all patients who receive at least one dose of the 2nd TPO-RA and have response assessed at 6 weeks after switching
 
Safety Set (SS): includes all patients who receive at least one dose of the 2nd TPO-RA after switching.
 
Efficacy analysis will be conducted on FAS and safety analysis on SS.

Table 1 Time and Events

Study procedures	Screening	During Treatment				Safety follow-up after treatment suspension/stop	End-of-study Visit
Visit schedule	-14~1d	Every week \pm 3d	Every 2 weeks	Every 4 weeks	Every 8 weeks	Every week \pm 3d	12 weeks \pm 7d

			±3d	±4d	±4d		
Written informed consent	X						
Demographics	X						
Medical history	X						
Physical examination	X	X				X	X
Ophthalmologic examination	X						X
CBC (incl. platelet count)	X	X ^{a, b}		X ^b		X ^e	X
Peripheral blood smear	X						
Liver function tests (ALT, AST, TB)	X		X ^c	X ^c		X ^d	X
Other clinical chemistry (incl. Cr)	X						X
Coagulation tests	X				X		X
Thyroid function test	X						
HBV, HCV, HIV testing	X						
ECG	X						
Ultrasound (spleen)	X				X		X
Chest X-ray	X						
Bleeding assessment	X	X				X	X

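### The sample-size sentence does not compute: 70% with a 95% CI of 50%–90% needs about 20 patients, not 80, and the precision of the per-sequence primary endpoint is never stated

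*Combined protocol and SAP*

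**What the plan says.** The Sample Size Justification in the combined protocol and SAP first says that the study is descriptive, does not compare the two switch groups, and therefore has no calculable sample size. It then gives three supports for 100 patients: a similar published study, a calculation, and the number expected to complete observation in a year and a half.

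The calculation is introduced by "Using the cross-sectional sampling method" and reads: "the estimated response rate of these two drugs is ~70% (95% CI, 50%-90%), the sample size would be 80". The last step is "100 patients' size was decided taking the 20% drop-out rate into consideration". No formula, half-width or design effect is given, and the text does not say whether the interval is for all patients pooled or for each sequence. Allocation is about "50 patients in each switch sequence but not a strict 1:1 ratio".

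The Endpoints section defines the primary endpoint as the proportion with complete response or response at 6 weeks "in the groups switch from rhTPO to eltrombopag and eltrombopag to rhTPO, respectively". For analysis, the Statistical Analysis section says "Categorical variables will be described as frequencies and percentages". It names no confidence interval for the response rates.

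**The concern.** In a descriptive study, precision is the natural justification for size. This sentence is the only one of the three supports that contains a rate, an interval and a drop-out factor, so it is where a reader looks to learn how precisely the primary rate will be estimated. Three things look wrong.

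- The interval and the number of patients do not correspond under the usual formula for one proportion.
- The number relates to one pooled rate, but the primary endpoint is two rates, one per sequence.
- The size is justified by a confidence interval that the analysis section does not plan to report.

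At stake is a misstated precision, and a primary result planned as a count and percentage with no interval. Whether the trial can run at its planned size is not in question.

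**Working it through.** **Inputs.** Response rate p = 0.70 and 95% interval 0.50–0.90, so half-width d = 0.20 (Sample Size Justification). Evaluable patients 80, drop-out 20%, total 100, about 50 per sequence (same section). Two-sided 95%, z = 1.96; the Statistical Analysis section also works two-sided ("statistical testing will be carried out bilaterally with significance level alpha=0.05").

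**Reproducing the plan's figures.** Formula: n = z² p(1−p) / d², with z² p(1−p) = 3.8416 × 0.21 = 0.8067.

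- Stated interval, d = 0.20: n = 0.8067 / 0.04 = 20.2, so 21. The plan says 80. Not reproduced.
- d = 0.10 (interval 60%–80%): n = 0.8067 / 0.01 = 80.7. This matches 80.
- Drop-out: 80 / (1 − 0.20) = 100. Reproduced.

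The fault therefore lies in pairing 50%–90% with 80. A total width of 20 points may have been written as plus or minus 20 points. That is an inference, and nothing below depends on it.

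**Could another method give 80 from the stated interval?**

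- One-sided 14.2; 99% level 34.8; continuity-corrected 25; worst case p = 0.5, 24.0.
- Wilson, Agresti-Coull or exact: 18 to 23 for a total width of at most 40 points, and 25 to 29 for both limits to lie within 50%–90%.
- One such interval per sequence: 2 × 21 = 42 evaluable, or 42 / 0.8 = 52.5, so 53 enrolled.
- Reading 20% as relative precision (d = 0.2 × 0.70 = 0.14): 41.2, or 2 × 42 = 84 for two sequences.

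None gives 80.

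**What the planned size delivers at a 70% rate.** Half-width = 1.96 × √(0.21 / n).

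| Evaluable n | Half-width (points) | Normal approximation | Wilson | Exact |
|---|---|---|---|---|
| 20 | 20.1 | 49.9%–90.1% | 48.1%–85.5% | 45.7%–88.1% |
| 40 (one sequence, even split, after drop-out) | 14.2 | 55.8%–84.2% | 54.6%–81.9% | 53.5%–83.4% |
| 50 (one sequence, no drop-out) | 12.7 | 57.3%–82.7% | 56.2%–80.9% | 55.4%–82.1% |
| 80 (pooled) | 10.0 | 60.0%–80.0% | 59.2%–78.9% | 58.7%–79.7% |

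**Uneven split.** The plan does not require 1:1. As assumed illustrations for 80 evaluable patients:

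- 50/30: the smaller sequence has half-width 1.96 × √(0.21 / 30) = 16.4 points.
- 60/20: half-widths are 11.6 and 20.1 points. The smaller sequence is then back at roughly 50%–90%.

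**The case against.** The strongest objection is that 50%–90% is attached to the assumed rate, so it may express uncertainty about that rate and not a precision target. The Study Rationale cites response rates after switching from 50% to 100%, which fits such a range. On that reading no target half-width is given, and saying that 80 is four times too many would not be fair. Against this, the text labels the range a 95% CI and derives 80 from the same sentence. If it is only a plausible range, the precision behind 80 is stated nowhere and the sentence still does not support the number. The defect changes from a wrong pairing to a missing input, and the correction needed is much the same.

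Four further points have merit.

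- **Direction.** Both 60%–80% and 56%–84% lie inside 50%–90%, so with a roughly even split the study is more precise than stated. This stands and limits the consequence.
- **Other support for 100.** The published precedent and the recruitment forecast also point to 100 patients. True, but neither states a precision.
- **The 40/40 split is an assumption.** This stands, and any restated precision should allow for imbalance.
- **Counts allow an interval to be derived, and the plan leaves room to choose descriptive methods.** True, but an interval for the primary result of a descriptive study should be planned, not left to the reader.

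**Conclusion.** The concern holds. Read as written, the sentence pairs an interval that needs about 20 patients with a sample size of 80, a factor of four. Eighty evaluable patients give about 60%–80% around 70%, and only for a pooled rate that is not the primary endpoint. About 40 evaluable per sequence give about 56%–84% (exact 53.5%–83.4%), a half-width of 14 points where 80 implies 10.

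These figures assume a true rate of 70%, 20% drop-out and an even split. If the rate were 50% or 90%, the half-width with 40 patients would be 1.96 × √(0.25 / 40) = 15.5 or 1.96 × √(0.09 / 40) = 9.3 points. The arithmetic error is certain if the range is the 95% CI that the text calls it. On the other reading, 80 has no stated derivation. The correction should be made, but it does not call for more patients.

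**What to change.** Keep 100 patients and change the text in two places.

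1. **Sample Size Justification.** State the formula, the intended half-width, and whether it applies to the pooled rate or to each sequence. Suggested wording: *Assuming a response rate of 70%, 80 evaluable patients give a two-sided 95% confidence interval of about 60% to 80% for the pooled rate. About 40 evaluable patients per sequence give about 56% to 84% for the primary per-sequence rate; with an uneven split the interval is wider in the smaller sequence. Allowing for 20% drop-out, 100 patients will be enrolled.* If 50%–90% was meant as a range of plausible rates, say so and remove the 95% CI label. Also reconcile the calculation with the opening statement that none is possible: no power calculation applies, but a precision calculation does.

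2. **Statistical Analysis.** State that the 6-week and 3-month response rates in each sequence will be reported as count, percentage and two-sided 95% confidence interval, and name the method (exact or Wilson).

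The cost is protocol and SAP wording plus a few lines of analysis code. Enrolment, visits and endpoints are unchanged. The sponsor would have to state openly that the primary rates are estimated to about ±14 points, not the ±10 that a sample of 80 implies.

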- Rate of response at 3 months after switching, according to the reasons of switching
- Proportion of patients who achieved, regained, and maintained response at 3 months after switching
- Time to response from 1st TPO-RA switching for patients who switch due to lack of efficacy
- Duration of response from 1st TPO-RA switching for patients who switch due to lack of efficacy

Duration of response is defined as the time from when CR or R is achieved/regained to the time of relapse.

- Proportion of patients with any bleeding (WHO bleeding scale grade 1–4¹¹) and clinically significant bleeding (WHO bleeding scale grade 2–4¹¹)
- Total score of bleeding calculated according to the Bleeding Rating System⁷
- Patient and physician's treatment preference

At 6 weeks after switching, patients will be asked whether they prefer to continue treatment with rhTPO or eltrombopag, or whether they had no preference¹². In addition, patients who prefer one TPO-RA over the other will be queried on the reasons of preference (Patient preference questionnaire attached as Appendix 1).

At 6 weeks after switching, physicians will also be asked whether they prefer to further treat the patient with rhTPO or eltrombopag, or whether they had no preference, taking into account the patient's preference, response, and tolerability¹².

At 3 months after switching, the measurement will be applied again.

- Safety of treatment

The safety of treatment will be determined from adverse events summarized by incidence and severity, and from clinical laboratory evaluations, physical examinations and ophthalmological examinations carried out during scheduled study visits.

Exploratory endpoints:

- Association between clinical characteristics and response after switching

The following clinical characteristics will be compared between responders and non-responders at 6 weeks and 3-month after switching, respectively: gender (male vs female), age at 1st TPO-RA, time from diagnosis to 1st TPO-RA, lines of previous therapy before 1st TPO-RA, maximum 1st TPO-RA dose received vs. not received, splenectomy status (yes vs no), switch sequence (rhTPO to eltrombopag or vice versa), switching behavior, switch due to efficacy vs non-efficacy issues, and 1st TPO-RA failure vs loss of response.

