Trial Design	
This is a prospective and retrospective observational study of switching eltrombopag and rh-TPO in Chinese adult patients with primary immune thrombocytopenia. A schematic illustration of the study design is shown as follows:
 
 
 
The study includes two stages: the retrospective stage and the prospective stage. Primary ITP patients who failed initial glucocorticosteroid treatment and receive rh-TPO and then switch to eltrombopag or vice versa will be screened for eligibility. Medical records will be retrospectively reviewed to collect baseline data before 1st TPO-RA administration, information on the 1st TPO-RA, as well as the reason for switch. Patients who meet the eligibility criteria upon medical history review and clinical evaluation will be enrolled at the time of switch. The switch procedure is as per physician preference and clinical practice.
 
After enrollment, patients will be followed up prospectively on administering the 2nd TPO-RA. Both rh-TPO and eltrombopag are applied according to the approved label and clinical practice, in considering the actual condition of a patient. For patients who switch from rhTPO to eltrombopag, platelet counts will be obtained weekly under stable dose and monthly following establishment of a stable platelet count ($\geq 50*10^9/L$ for at least 4 weeks), while platelet counts will be obtained at least once a week during dose adjustment. Liver function tests (ALT, AST, TB) will be performed monthly under stable dose but increased to bi-weekly during dose adjustment. For patients who switch from eltrombopag to rhTPO, platelet counts will be obtained every other day during initial treatment and weekly during maintenance therapy.
 
Platelet counts will be obtained at least once a week for all patients who suspend/stop their 2nd TPO-RA, while liver function tests will be performed bi-weekly in patients who suspend/stop eltrombopag as their 2nd TPO-RA. Once treatment is resumed, monitoring of platelet counts and liver function will be performed as per during treatment administration. An end-of-study visit will be performed for all patients at

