Bone marrow aspirate	As clinically required.						
Pregnancy test	X						X
Concomitant therapy ^f	X	X				X	X
AE/SAE assessment	X	X				X	X

- a. For patients who switch from eltrombopag to rhTPO, CBC should be performed every other day during initial treatment and weekly during maintenance therapy.
- b. For patients who switch from rhTPO to eltrombopag, CBC should be monitored weekly until stable platelet count is observed ($\geq 50*10^9/L$ for at least 4 weeks), then CBC will be monitored every 4 weeks. Platelet counts will be obtained at least once a week during dose adjustment.
- c. For patients who switch from rhTPO to eltrombopag, liver function tests (ALT, AST, TB) will be performed every 4 weeks under stable dose but increased to every 2 weeks during dose adjustment.
- d. For patients who switch from rhTPO to eltrombopag, liver function tests (ALT, AST, TB) will be performed every 2 weeks after treatment suspension/stop.
- e. The frequency of platelet monitoring can be increased to twice weekly for patients who suspend/stop eltrombopag due to platelet counts $>250*10^9/L$.
- f. Record concomitant ITP treatment (including rescue medications), anticoagulants, and NSAIDs.

Table 2 Dose Adjustment Guidelines of Eltrombopag

After initiating eltrombopag, the dose should be adjusted to achieve and maintain a platelet count $\geq 50*10^9/L$ as necessary to reduce the risk of bleeding. A daily dose of 75 mg must not be exceeded.

Clinical haematology and liver tests should be monitored regularly throughout therapy with eltrombopag and the dose regimen of eltrombopag modified based on platelet counts as outlined in **Table 2**.

During therapy with eltrombopag, platelet counts should be assessed weekly until a stable platelet count ($\geq 50*10^9/L$ for at least 4 weeks) has been achieved. Platelet counts should be obtained monthly thereafter.

Platelet count	Dosage adjustment or response
$<50*10^9/L$ following at least 2 weeks of therapy	Increase daily dose as per 25mg. Monitor platelet count at least once a week, wait for 2 weeks, assess the treatment effect after dose increase, and consider whether further dose adjustment is needed. Maximum daily dose is 75mg per day.
$\geq 50*10^9/L$ to $\leq 150*10^9/L$	Use lowest dose of eltrombopag and/or concomitant ITP treatment to maintain platelet counts that avoid or reduce bleeding.

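### Platelet-count schedules differ by switch sequence, so a between-sequence log-rank test on first-detection dates makes response look faster on rhTPO; duration of response is affected less

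*Combined protocol and SAP*

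**What the plan says.** The Statistical Analysis section has one sentence on these endpoints: it plans Kaplan-Meier curves "with log-rank test for between-group comparison". The same section adds that "statistical testing will be carried out bilaterally with significance level alpha=0.05". It does not name the groups for the log-rank test.

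The endpoints concerned are time to response and duration of response, both secondary and both restricted to patients who switched for lack of efficacy. On the second, the Endpoints section states: "Duration of response is defined as the time from when CR or R is achieved/regained to the time of relapse". Response and relapse are defined by platelet thresholds, doubling of the baseline count, and bleeding.

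The Trial Design section sets the count schedules:

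- rhTPO as second drug: "platelet counts will be obtained every other day during initial treatment and weekly during maintenance therapy". The Investigational Drug Administration section limits initial treatment to 14 days.
- Eltrombopag as second drug: "platelet counts will be obtained weekly under stable dose and monthly following establishment of a stable platelet count", where stable means at least 50×10⁹/L for at least 4 weeks.

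Footnotes a and b to Table 1 repeat this difference. The document gives no event-dating rule, common assessment grid, interval-censored method or sensitivity analysis for the unequal schedules.

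**The concern.** An event that depends on a platelet count can be dated only on a day when blood is drawn. In the first two weeks, when many responses may occur, one sequence is sampled every 2 days and the other every 7. Later, the rhTPO sequence stays weekly while stable eltrombopag patients move to every 4 weeks.

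If the first date on which the criterion is seen is taken as the event date, the gap between true and recorded times differs by sequence. Response is recorded earlier on rhTPO, and relapse is recorded later on eltrombopag. A descriptive reader would see this in the curves and medians, and a log-rank test could call it a drug difference. Two named secondary endpoints are at stake.

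**Working it through.** The plan states no power, event count or hazard ratio for these endpoints, so it has no figure to reproduce. The check asks what the planned analysis would show if both sequences had the same true event times.

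**Inputs from the document**
- Schedules as above; follow-up 3 months (84 days); two-sided alpha 0.05.
- About 50 patients per sequence and 20% dropout, so about 40 evaluable.
- Planning response rate about 70%. A cited series reports 57.8% among efficacy switchers.
- The document plans no share of lack-of-efficacy switchers. In a cited retrospective series it was 23/46 = 50%, giving 50 × 0.5 = 25 or 40 × 0.5 = 20 per sequence.

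**Assumptions**
- True median times to response among responders of 5 to 14 days, Weibull shape 1 (exponential) or 2.
- True median durations of 21 to 84 days, exponential.
- Visit windows, confirmatory counts and dropout were not modelled.

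**Rule applied.** Recorded date = first scheduled count on or after the true date. The rhTPO grid is days 2, 4, …, 14, then 21, 28, …; the eltrombopag grid for response is days 7, 14, 21, ….

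**Time to response: detected medians.** Take exponential times with a median of 7 days, so F(t) = 1 − 2^(−t/7).
- rhTPO grid: F(6) = 0.448 and F(8) = 0.547, so the detected median is day 8.
- Weekly grid: F(7) = 0.500 exactly, so a sample median falls on day 7 or day 14 about equally often and averages (7 + 14)/2 = 10.5 days.

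Simulation with 60% responders and 20-40 per sequence gave averages of 8.2-8.5 and 10.5-10.7 days.

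**Time to response: delay and false positives.** Over all scenarios the mean detection delay is 1.0-2.4 days on the rhTPO schedule and 3.5-4.1 days on the eltrombopag schedule. Log-rank rejection with no true difference, 70% responders and 3,000 runs (each range covers the two Weibull shapes):

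| True median | 20 per sequence | 25 per sequence | 50 per sequence | Common weekly grid, all sizes |
|---|---|---|---|---|
| 5 days | 10.5-16.5% | 11.8-18.3% | 20.1-31.0% | 4.8-5.7% |
| 7 days | 7.2-10.6% | 8.0-12.4% | 10.7-22.2% | 4.7-6.4% |
| 10 days | 5.4-8.4% | 6.0-7.9% | 6.9-11.4% | 4.3-5.7% |
| 14 days | 5.2-6.1% | 5.6-5.7% | 5.4-5.5% | 4.9-6.1% |

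The simulation error at 5% is √(0.05 × 0.95/3000) = 0.4 points. At medians of 5 to 7 days almost all excess rejections favour rhTPO as faster. With 60% responders, exponential times and a 7-day median, rejection is 6.2-7.2% at 20-25 per sequence. Together with the table this gives about 6-12%. The return to nominal on a common grid shows that the schedule is the cause.

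**Duration of response.** With an assumed true median of 30 days and 15 or 25 responders per sequence (1,000 runs), adding the document's own limits on the 4-weekly gap one at a time gives:

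| Eltrombopag counts after response | Detected median, rhTPO vs eltrombopag | Rejection |
|---|---|---|
| All patients 4-weekly, no week-6 count | about 34 vs 44 days | 8-9% |
| Week-6 count added | 34-35 vs 41-42 days | not recorded |
| Also only 60% reach 4-weekly counts (assumed) | 34 vs 38 days | 5-6% |
| Also 40% of relapses seen at weekly visits (assumed) | 34-35 vs 36-37 days | 4-5% |

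A separate simulation with all eltrombopag patients 4-weekly put the mean delay in dating relapse at 3.3-3.4 days on rhTPO and 7.5-8.7 days on eltrombopag. Rejection was 6.9-9.4% at a 21-day median, 4.9-6.6% at 42 days and 4.3-5.0% at 84 days. Later dating of response on eltrombopag offsets part of its later dating of relapse.

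**The case against.** **The comparison is inferred.** The log-rank sentence is generic, the two endpoints are not listed by sequence, and the Sample Size Justification says the study does not aim to compare efficacy between the switch groups. The test could be meant for 1st TPO-RA failure versus loss of response. A comparison within one sequence would be largely free of the problem. The plan also never states that detection dates are event dates; that is only the default when nothing is specified. This stands as a limit. However, the document itself calls the sequences groups, a test at 0.05 is planned, and curves or medians shown by sequence are shifted whether or not a p-value is reported.

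**Duration may look like the worse problem**, because a weekly versus 4-weekly gap is wider than 2 versus 7 days. The document does not support that reading:
- The 4-weekly interval begins only after at least 4 weeks at 50×10⁹/L or more, so responders at 30-50×10⁹/L stay weekly.
- Counts are at least weekly during dose adjustment and suspension.
- Response must be assessed at 6 weeks, which breaks the gap.
- Bleeding counts as relapse and is assessed weekly in both sequences.

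A reader might also suppose that short relapses slip between 4-weekly counts. Rejection of 10-19% appears only if relapses are assumed to last about 14 days and resolve unseen, and no figure in the document supports that assumption.

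**Visit windows** of ±3 days blur the weekly grid but do not turn weekly counts into every-other-day counts.

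**Conclusion.** The concern holds, mainly for time to response. Applied between sequences on first-detection dates, the planned analysis favours rhTPO by about 2.5 days in detected median (8 versus 10.5) at an assumed true median of 7 days. The false-positive rate is about 6-12% with 20-25 lack-of-efficacy switchers per sequence. It rises with faster response or larger groups and is near nominal by a 14-day median.

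For duration, the firmer point is the later dating of relapse in stable eltrombopag patients: about 34 versus 36-44 days at an assumed true median of 30 days. The log-rank test is inflated little, about 4-9%.

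These sizes rest on assumed event times, an assumed share of lack-of-efficacy switchers and an assumed share reaching 4-weekly counts; the document gives none of these for this study. The direction of the bias does not depend on them. A reader might infer that the main result is compromised. It is not: the primary endpoint is a response rate at a fixed 6 weeks. The change is worth making, but it concerns two unpowered secondary endpoints in a descriptive study.

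**What to change.** In the Statistical Analysis section:

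1. Name the groups for the log-rank comparison and state how event dates are assigned.
2. Derive time to response in both sequences from a common weekly grid, using only the count nearest each weekly time point.
3. Estimate duration of response as interval-censored between the last count without relapse and the first count with relapse, taking its start from the same weekly grid. A fixed common grid will not serve for relapse, because the eltrombopag interval depends on each patient's stability and dose changes, and 4-weekly counts cannot be made weekly afterwards. State the assumption that the count interval is non-informative given earlier counts.
4. Keep the analysis of all counts as a sensitivity analysis.
5. Do not report a between-sequence log-rank p-value from the unharmonised dates.

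The cost is SAP wording and a little programming. Some early rhTPO counts go unused in the main time-to-response analysis. No change to clinical monitoring is needed.
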